2.1 PROTOCOL SYNOPSIS

The Protocol Synopsis is in Appendix 1 and the Schedule of Assessments in Appendix 2 For additional details, please see the CSP Version 3, 28 June 2018 (and its Appendices).

2.2 OUTCOME MEASURES

This trial will evaluate the efficacy and safety of pirfenidone in patients with fibrosing interstitial lung disease (ILD) who cannot be classified with moderate or high confidence into any other category of fibrosing ILD by multidisciplinary team (MDT) review ("unclassifiable" ILD).

The primary analysis of the primary and secondary efficacy outcome measures of this study is planned to be performed when the last patient reached the date of the last follow-up visit after end of the double-blind treatment period.

Pirfenidone — F. Hoffmann-La Roche Ltd

2.2.1 Primary Efficacy Outcome Measures

The primary efficacy objective for this trial is to evaluate the effect of pirfenidone vs. placebo on lung function parameters on the basis of Forced Vital Capacity (FVC) measurements. FVC will be measured daily by the patients by use of a handheld spirometry.

The primary efficacy endpoint is defined as:

 rate of decline in FVC in mL measured by daily handheld spirometer over the 24week double-blind treatment period.

2.2.2 Secondary Efficacy Outcome Measures

The secondary efficacy objective for this trial is to evaluate the efficacy of pirfenidone compared with placebo from baseline until Week 24 on other functional parameters, outcomes, and patient reported outcomes (PROs).

The following endpoints will be analyzed:

- Change in percent predicted FVC and in mL measured by spirometry during clinic visits
- Categorical change in FVC of >5% (absolute change in percent predicted and relative change in mL), measured by spirometry during clinic visits
- Categorical change in FVC of >10% (absolute change in percent predicted and relative change in mL), measured by spirometry during clinic visits
- Change in percent predicted diffusing capacity of the lung for carbon monoxide (DLco)
- Change in (6-minute walk distance) 6MWD in meters
- Change in University of California, San Diego Shortness of Breath Questionnaire (UCSD-SOBQ) score
- Change in score in Leicester Cough Questionnaire
- Change in cough visual analog scale
- Change in total and sub-scores of the St. George's Respiratory Questionnaire (SGRQ)
- Non-elective hospitalization, both respiratory and all cause
- Incidence of, and time to first, investigator-reported acute exacerbations
- Progression free survival (PFS), defined as the time to the first occurrence of a >10% absolute decline in percent predicted FVC (measured during a clinic visit), a >50 m decline of 6MWD, or death
- PFS, alternatively defined as the time to the first occurrence of a >10% relative decline in FVC (measured during a clinic visit), non-elective respiratory hospitalization, or death
- Time to death from any cause

Pirfenidone — F. Hoffmann-La Roche Ltd

• Time to death from respiratory diseases

2.2.3 Exploratory Efficacy Outcome Measures

One exploratory objective for this trial is to evaluate the role of mycophenolate mofetil/sodium or mycophenolic acid (MMF) treatment in ILD and to evaluate potential biomarkers associated with fibrosis and ILD.

The exploratory endpoints associated are:

- Efficacy and safety data from subgroups of patients who did or did not receive MMF treatment
- Biomarker data from plasma, serum, and whole blood ribonucleic acid (RNA) and deoxyribonucleic acid (DNA) samples

2.2.4 Safety Outcome Measures

The safety objective for this trial is to evaluate the safety of pirfenidone vs. placebo by investigating the following endpoints:

- Nature, frequency, severity, and timing of treatment-emergent adverse events
- Dose reductions and treatment interruptions
- Clinical laboratory test results
- 12-lead ECGs
- Withdrawals from trial treatment or trial discontinuations

All analyses with regard to the safety outcome measures will be performed from the date of first randomized treatment intake until 28 days after the last positive dose during the double-blind randomized treatment period.

2.3 DETERMINATION OF SAMPLE SIZE

The purpose of this trial is hypothesis generation regarding the efficacy of pirfenidone vs. placebo on lung function parameters on the basis of rate of decline in FVC, as measured by daily handheld spirometry.

A total sample size of approximately 250 patients is planned, and patients will be randomized in a 1:1 ratio. The randomization will be stratified by concomitant MMF treatment (yes/no), the presence/absence of IPAF as defined by the MDT.

The planned sample size is based on the statistical hypothesis of the primary endpoint and assumes 80% power and a two-sided significance level of 5% using a student's t-test. It is assumed, after inspection of historical data, that FVC decline in the placebo arm is 85 mL with a common standard deviation of 70 mL, which can be reduced to 60 mL with a common standard deviation of 70 mL in the pirfenidone arm. In this

Pirfenidone — F. Hoffmann-La Roche Ltd

scenario, 125 patients per treatment arm are needed to detect this treatment effect with 80% power.

These assumptions are based upon the following considerations: in IPF, the annual rate of decline of FVC is approximately 200 mL. Owing to the fact that patients with unclassifiable ILD have rates of disease progression in the range of patients with IPF, albeit with a lower mortality rate (Ryerson et al. 2013), a similar decline rate of 200 mL/year, equivalent to a 100 mL decline over a treatment period of 24 weeks, can be expected. However, a yet unknown proportion of patients in this trial will be treated concomitantly with MMF. In a previous study of CTD-ILD (Fischer et al. 2013), MMF was found to have beneficial effects on lung functions in these patients. While CTD-ILD is a distinct entity from the current trial population, both conditions may share some autoimmune features. Therefore, assuming a smaller FVC decline of 85 mL in the placebo arm compared with 60 mL in the pirfenidone arm over the 24-week double-blind treatment period appears justified. In addition, the potential confounding effect of concomitant MMF therapy in these patients justifies stratification to ensure equal distribution of patients who receive and do not receive treatment with MMF.

2.4 INTERIM ANALYSIS

There are no planned interim efficacy analyses for this trial.

3. STUDY CONDUCT

The study conduct is described in Section 2.

3.1 RANDOMIZATION, BLINDING AND UNBLINDING PROCEDURES

Patients will be randomized 1:1 to receive either pirfenidone or placebo. The randomization process will be conducted using a validated interactive voice or webbased response system (IxRS). To guard against systematic selection bias and ensure comparability of treatment arm, the randomization will be stratified by concomitant MMF treatment (yes/no), the presence/absence of IPAF as defined by the MDT.

To maintain the double-blind nature of the trial, the pirfenidone and placebo treatments will be identical in appearance (see CSP Section 4.3.1.1).

The investigational site personnel and the patients will be blinded to treatment assignment following randomization. The iDMC and any personnel performing any interim analysis (as applicable) will be unblinded to the treatment throughout the trial.

3.2 INDEPENDENT REVIEW FACILITY

An independent review of home spirometry date (FVC (mL)) took place after it was recognized that the data collected for the primary analysis of this study was jeopardized by incorrect readings of the device and implausible values were collected due to technical issues. A new data set is available now after doing the reread of the FVC data and will be analyzed together with the previous data set collected to investigate the impact of the new data on the statistical results of this endpoint.

Pirfenidone — F. Hoffmann-La Roche Ltd

More details are provided in section 4.5.2.

3.3 DATA MONITORING

An independent Data Monitoring Committee (iDMC) will review safety data and advice on study conduct at least three times during the study. Efficacy data will only be provided if requested by the iDMC. A first meeting is planned 6 months after start of recruitment, and subsequently at 12 and 18 months. Details on procedures and safety review by the iDMC are described within an iDMC charter.

4. STATISTICAL METHODS

Categorical data will be summarized using frequencies and percentages (including a category for missing, if appropriate). Percentages will be based on the number of patients in each treatment arm for the analysis population, if not otherwise specified.

Continuous endpoints will be summarized using descriptive statistics (mean, standard deviation, minimum, 25th and 75th quartiles, median, and maximum).

Where data will be summarized over time, the following timepoints will be presented as applicable: Baseline, Week 4, Week 8, Week 12, Week 16, Week 20, Week 24, Week 28 (if applicable) and early discontinuation visit.

Data analysis of data collected during the 12-month safety follow-up period will be described in section 4.7.

Where applicable other analysis methods will be specified below.

4.1 ANALYSIS POPULATIONS

4.1.1 Intent-to-treat Population

The intent-to-treat (ITT) population is defined as all randomized patients. Patients in the ITT population will be assigned to treatment arm as randomized (planned treatment). The ITT population is the primary analysis population for all efficacy analyses. The time period for all efficacy analyses is defined from date of randomization until the treatment completion date of the double-blind treatment period or the date of early discontinuation collected on the early treatment discontinuation eCRF page in case a patient does not complete the planned 24 weeks of double-blind treatment.

4.1.2 Per Protocol Population

Not applicable.

4.1.3 Safety Population

The safety population is defined as all patients with at least one intake of pirfenidone or placebo, i.e. at least one record in the drug-log of the double-blind period with a non-zero dose. Patients in the safety population will be assigned to treatment arm according to the actual treatment they received.

Pirfenidone — F. Hoffmann-La Roche Ltd

4.1.4 Safety Follow-up Population

For the 12-month safety follow-up period, the safety follow-up population will be defined as all patients who have received at least one dose of pirfenidone after the randomized treatment end plus 28 days.

Safety analyses for the 12-month follow-up period will be performed from the date of the first pirfenidone drug intake during safety follow-up period up to the study completion/discontinuation visit.

4.2 TRIAL PERIODS, OBSERVATION AND ANALYSIS TIMES

Where durations are to be calculated (e.g. treatment duration), these will be derived based on the interval in days (end date – start date + 1) and converted to months and years if needed, using 30.4375 and 365.25, respectively, as denominator if not otherwise specified.

For the investigational medicinal product (IMP) exposure, treatments administered from the date of first randomized pirfenidone/placebo treatment up to the date of completion of double-blind treatment or date of early treatment discontinuation, will be regarded.

For drug safety, analyses will be restricted to AEs or assessments that occurred from the first day of randomized treatment until the date of last positive dose of randomized treatment plus 28 days.

Safety analyses for the 12-month follow-up period will be performed using the time window from the safety follow-up period start up to the study completion/discontinuation visit.

4.2.1 Study Days

Study days will be defined as the number of days since randomization, and is calculated as:

- Study day = Assessment date randomization date + 1, for assessments on or after the randomization date.
- Study day = Assessment date randomization date, for assessments before the randomization date.

The day of randomization will be study day 1.

Pirfenidone — F. Hoffmann-La Roche Ltd

4.2.2 Baseline and Screening Observations

Table 1 Definition of Baseline and Screening Observations

| | Definition |
|----------------|---|
| Baseline data | Baseline is defined as the last valid assessment prior to first intake of randomized study drug (pirfenidone/placebo). |
| | This may not be the same as the Day 1 (Week 1) visit as per eCRF. In case that Day 1 (Week 1) visit data is missing and the randomized treatment is given, data from the screening period will be used as baseline. In addition, if randomized treatment is not given then baseline will be defined as the last valid assessment collected either screening or day 1. |
| | Generally, it is assumed that measurements referring to the Day 1 (Week 1) visit have been performed before randomized study drug (pirfenidone/placebo) was given. |
| | Adverse events occurring on the date of first randomized pirfenidone/placebo treatment will not be considered baseline, but treatment-emergent. |
| Screening data | Screening measurements are all the measurements performed before the randomization date. |

4.2.3 On-treatment Assessments for Efficacy Analyses (Double-blind Treatment Period)

For efficacy analyses, on-treatment assessments will be the assessments performed on or after the randomization date until the double-blind treatment completion or discontinuation date.

4.2.4 On-treatment Assessments for Safety Analyses (Double-blind Treatment Period)

For safety analyses, on-treatment assessments will be the assessments performed on or after the first dose of randomized pirfenidone/placebo date until the last positive dose of randomized treatment plus 28 days.

4.2.5 On-treatment Assessments (12-Month Safety Follow-up Period)

Details of all data recorded during the 12-month safety follow-up period will be presented. This period starts on the day of the first positive dose of pirfenidone after the 28 days follow-up visit for patients who completed the double-blind treatment period without being discontinued the study. The safety follow-up period ends with the study completion/discontinuation visit, with a maximum duration of 12 months plus 28 days.

Pirfenidone — F. Hoffmann-La Roche Ltd

Safety follow-up analyses will be presented separately from double-blind treatment phase ones.

4.2.6 Cut-off points

The clinical cut-off for the primary analysis will occur when the last patient has completed the final safety Follow-up Visit, 28 days after the double-blind treatment period.

There will be a second cut-off for the final analysis when all patients have completed the 12-month safety follow-up period.

For each patient the total length of the trial is expected to be up to a maximum of 91 weeks. The trial duration includes the washout period of up to 4 weeks, the screening period of up to 3 weeks, the double-blind treatment period of 24 weeks, the follow-up period of 4 weeks, the open-label safety follow-up period up to 12 months (52 weeks) plus 28 days and a final safety Follow-up Visit 4 weeks after the last dose.

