4.3.4 Continued Access to Pirfenidone

After completion of the double-blind treatment period, the Sponsor will offer the possibility to the patients to receive continued access to pirfenidone in a safety follow-up period of up to 12 months, within this clinical trial protocol. A final Follow-up Visit will be performed at the end of the safety period, 28 days after the last open-label dose.

At the end of the 24-week double-blind treatment period, in order to maintain blinding, all patients will discontinue treatment over a 28-day period and return for the Follow-up Visit.

For patients who could benefit from participating in the 12-month safety follow-up period, according to the investigator's judgment, open-label pirfenidone will be started on the 28-day Follow-up Visit, using the titration schedule in [Table 2](#) . During the 12-month safety follow-up period, initially, patients will be evaluated at monthly visits for the first 6 months. At the end of the first 6 months, patients will be evaluated at each site visit occurring approximately every 3 months until the end of the safety follow-up period. In addition, at the end of the first 6 months, patients will perform home pregnancy tests at each month where there is no site visit. Patients will be provided with home pregnancy test kits and will be instructed to contact the site immediately should the test result be positive. In such cases, the patient must visit the site for a confirmatory serum pregnancy test. Refer to Schedule of Assessments for the assessments to be performed during this safety follow-up period ([Appendix 1](#)). The dose of pirfenidone used during the safety follow-up period is in accordance to section 4.3.2.1.

Following the end of the 12-month safety follow-up period, the Sponsor will offer post-trial access to the trial treatment (pirfenidone), free of charge, to eligible patients in accordance with the Roche Global Policy on Continued Access to IMP, as outlined below.

A patient will be eligible to receive Pirfenidone (Esbriet®) after completing the trial if all of the following conditions are met:

- The patient has a life-threatening or severe medical condition and requires continued trial treatment for his or her well-being
- There are no appropriate alternative treatments available to the patient
- The patient and his or her doctor comply with and satisfy any legal or regulatory requirements that apply to them.

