Whole blood for PAX gene biomarker assessment			x	x		x			x	x			
Concomitant medications ^r	x	x	x	x	x	x	x	x	x	x	x	x	x
Adverse events ^s		x	x	x	x	x	x	x	x	x	x	x	x
Whole blood sample for RBR (optional) ^t			x										

6MWD=6-minute walk distance; ALT=alanine aminotransferase; AST=aspartate aminotransferase; BUN=blood urea nitrogen; DLco=diffusing capacity of the lung for carbon monoxide; ECG=electrocardiogram; eCRF=electronic case report form; FEV₁=forced expiratory volume in 1 second; FVC=forced vital capacity; IMP=investigational medicinal product; LDH=lactate dehydrogenase; LFT=liver function test; PRO=patient-reported outcome; RBC=red blood cell; RBR=Research Biosample Repository; SGRQ=St. George's Respiratory Questionnaire; SOBQ=Shortness of Breath Questionnaire; UCSD=University of California, San Diego; WBC=white blood cell

Notes: all assessments should be performed within 7 days of the scheduled visit, unless otherwise specified.

- ^a Patients will be required to taper and/or discontinue all prohibited medications in the 28 days prior to the start of screening during the washout period. Patients not taking a prohibited medication will forgo the washout period and directly enter screening.
- ^b Patients who discontinue trial treatment prematurely will return to the site (clinic) for an Early Treatment Discontinuation Visit 28 (± 5) days after the last dose of the double-blind treatment, thus ending their participation in the trial. For patients who end their participation in the double-blind treatment period due to unblinding, they may be offered to continue into the open-label period according to the investigator's judgment. These patients will attend the Early Treatment Discontinuation Visit (28 (± 5) days after the last dose of the double-blind treatment) and on the same day begin their participation in the 12-month open-label pirfenidone safety follow-up period.

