- ^k Only LFTs (AST, ALT, bilirubin, and alkaline phosphatase) will be conducted at these visits. During the Safety Follow-up period, LFTs will be performed every month during the first 6 months and subsequently at each visit occurring approximately every 3 months thereafter, until the end of this period.
- ^l All women of childbearing potential will have a serum pregnancy test at screening. Urine pregnancy tests will be performed at the specified subsequent visits. If a urine pregnancy test is positive, it must be confirmed by a serum pregnancy test. During the Safety Follow-up period, urine pregnancy tests will be performed every month during the first 6 months at each site visit. Urine pregnancy tests will continue to be performed on a monthly basis during the remainder of the Safety Follow-up period with patients performing the test at home (using kits provided by the site) during months where there is no site visit and at each site visit occurring approximately every 3 months. Patients will be instructed to contact the site immediately in case the result of the home pregnancy test is positive. In such cases, the patient must visit the site for a confirmatory serum pregnancy test.
- ^m Open-label treatment with pirfenidone will be started at this visit, if the patient requests continued treatment with pirfenidone.
- ⁿ Handheld spirometry will be conducted by the patient every day in a seated position.
- ^o To provide handling evaluations and quality assurance for the daily spirometer assessments, nursing visits to the patient's home (or at another suitable location) will occur at least three times during the trial, namely between Weeks 1 and 4, between Weeks 8 and 12, and between Weeks 16 and 20. Additional home nursing visits may be conducted according to the investigator's judgment.
- ^p 6-Minute Walk Distance (6MWD) is used to evaluate the functional capacity of patients with lung disease.
- ^q Questionnaires will be self-administered prior to the patient receiving any information on disease status and prior to the performance of non-PRO assessments. Refer to [Appendix 2](#) for copies of the questionnaires and a brief description.
- ^r Includes any medication (e.g., prescription drugs, over-the-counter drugs, vaccines, herbal or homeopathic remedies, nutritional supplements) used by a patient from the washout period until 28 days after the last dose of trial treatment.

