Non serious Treatment-emergent Adverse Events with >5% frequency will be also presented by SOC and PT. In addition, Serious Treatment-emergent Adverse Events, Fatal serious TEAEs and serious TEAEs related to pirfenidone or placebo will be presented in the same table by SOC and PT.

A summary table presenting the numbers and frequency of patients with TEAEs by most extreme CTCAE Grade (Grade 1, Grade 2, Grade 3, Grade 4 and Grade 5) will be provided for each SOC and PT by treatment arm. In case the most extreme intensity is missing, it will be replaced by the initial intensity. If both most extreme and initial intensity are missing, the AE will be included in the Grade ≥3 category and a category for "missing" will be added.

Further, Kaplan-Meier curves for time to onset of first adverse event of the most relevant related TEAEs will be provided by treatment arm when the number of events are enough to do the analyses. These will include the following PTs or groups of AEs: Nausea, Diarrhoea, Weight decreased, Fatigue, Decreased appetite, and photosensitivity, or rash. In addition, the analysis will be done for the SOC GI.

All adverse event data will be listed by patient number and study day of onset including a flag variable for identifying the period of the event (double-blind treatment period or safety follow-up period). If the AE does not belong to any of the periods, the period flag will be missing.

In addition, for regulatory purpose two additional tables will be provided:

Pirfenidone — F. Hoffmann-La Roche Ltd

Frequency of adverse drug reactions occurring in patients treated with Esbriet (Pirfenidone) in clinical trials

TEAEs from day 1 of dosing until 168 days for MA39189 will be compared with the data from the phase III studies CAPACITY1 and 2 and ASCEND (restricted to first 168 days after first dose). The frequency of patients with related AEs (ADR) will be presented by System Organ Class and will be classified by their occurrences into

- Very common ((>=10% incidence rate)
- common ((>= 1% to <10% incidence rate)
- uncommon (>= 0.1% to <1% incidence rate)
- rare (>= 0.01% to <0.1% incidence rate)

Patients who withdrew from treatment during first 168 days of dosing will be censored at day of withdrawal for this analysis.

Rates of Adverse events per 100 patient years

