4.2.5 On-treatment Assessments (12-Month Safety Follow-up Period)

Details of all data recorded during the 12-month safety follow-up period will be presented. This period starts on the day of the first positive dose of pirfenidone on or after the 28 days follow-up visit for patients who completed the double-blind treatment period without being discontinued the study. The safety follow-up period ends with the study completion/discontinuation visit, with a maximum duration of 12 months plus 28 days. Safety follow-up analyses will be presented separately from double-blind treatment phase ones.

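### The SAP gives open-label entrants who did not complete double-blind treatment no period start, and its boundary wording can misattribute events around the first open-label dose

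*SAP*

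**What the plan says.** **When open-label drug starts.** For patients who finish double-blind treatment, Protocol 4.3.4 says "open-label pirfenidone will be started on the 28-day Follow-up Visit". Appendix 1, footnote m, agrees: "Open-label treatment with pirfenidone will be started at this visit, if the patient requests continued treatment with pirfenidone".

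**Who else may enter.** Under Protocol 4.2, an unblinded patient is withdrawn from the double-blind period. If unblinding shows that the patient was not on pirfenidone, and the investigator has no remaining safety concern, open-label treatment may be offered. Appendix 1, footnote b, places the Early Treatment Discontinuation Visit at 28 (±5) days after the last double-blind dose. It says that these patients "on the same day begin their participation in the 12-month open-label pirfenidone safety follow-up period".

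**How the SAP defines the open-label period.** Version 3.0, section 4.2.5: "This period starts on the day of the first positive dose of pirfenidone after the 28 days follow-up visit for patients who completed" double-blind treatment. Version 2.0 had "first positive dose of pirfenidone on or after the 28 days follow-up visit", and was also limited to completers.

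**How the SAP defines the population.** Section 4.1.4 takes all patients who have "received at least one dose of pirfenidone after the randomized treatment end plus 28 days". It is not limited to completers. Its analysis window runs from the first pirfenidone intake within the safety follow-up period.

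**Which AEs count.** Section 4.7 counts AEs that start or worsen from the period start onward and shows them by randomised arm. Section 4.6.2 ends the double-blind treatment-emergent (TEAE) window at the last positive randomised dose plus 28 days. It lists every AE with a period flag: "If the AE does not belong to any of the periods, the period flag will be missing". Its post-treatment category covers only patients who do not enter open-label.

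**The concern.** Three SAP definitions (4.1.4, 4.2.5 and 4.7) have to agree with each other and with when the protocol gives the first open-label dose. They do not. One permitted group of entrants has no period at all. For everyone else, the boundary wording leaves the first open-label day open to interpretation, and the population rule uses a fixed day count instead of the dose itself.

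At stake is the attribution of AEs at the start of open-label treatment. A reaction to open-label pirfenidone may be tabulated under the randomised arm in the double-blind tables, or may reach no table. For unblinded entrants, who by Protocol 4.2 had not received pirfenidone, this is first exposure to the drug. Counting them in the denominator without their events also lowers the reported open-label rates.

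**Working it through.** **Inputs.** Appendix 1 puts Week 24 at Day 168 and the Follow-up Visit at Day 196 ±5. The Early Treatment Discontinuation Visit is 28 (±5) days after the last double-blind dose (Appendix 1, footnote b; Protocol 4.2 words this timing differently, and I use Appendix 1). Let L be the study day of the last positive randomised dose and V the day open-label drug starts.

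**1. The plan's own figure.** 168 + 28 = 196, as scheduled. The ±5 window gives V = 191 to 201, which is 11 possible days.

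**2. Unblinded entrants.** They have not completed double-blind treatment, and their entry visit is not the 28-day Follow-up Visit. Section 4.2.5 therefore yields no start date, and no AE can satisfy 4.7. If open-label drug starts d days after the last randomised dose, the number of open-label days still inside the double-blind TEAE window is max(0, 28 − d + 1):

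| d | 23 | 24 | 25 | 26 | 27 | 28 | 29 to 33 |
|---|---|---|---|---|---|---|---|
| Days | 6 | 5 | 4 | 3 | 2 | 1 | 0 |

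AEs with onset on those days are tabulated as double-blind. All later ones are only listed, with the flag missing. Suppose k such patients are in the 4.1.4 population, y of them have an event, and x of the other N patients do. The table then shows x/(N + k) where it should show (x + y)/(N + k).

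**3. First open-label day, completers.** If *after* is read by date, the first qualifying dose falls no earlier than V + 1, so an AE with onset on V is outside the open-label period for all 11 values of V. It is in the double-blind window when V ≤ L + 28:

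| L | Onset on V is in the double-blind tables | Onset on V is in neither set of tables |
|---|---|---|
| 168 | V = 191–196 (6 of 11 days) | V = 197–201 (5 of 11 days) |
| 167 | V = 191–195 (5 of 11 days) | V = 196–201 (6 of 11 days) |

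L = 167 is an assumption, tried because Appendix 1 marks no treatment administration at Week 24. These are counts of possible visit days, not shares of patients.

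**4. Population rule.** Take randomised treatment end as Day 168. Section 4.1.4 then needs a dose on Day 197 or later. A patient who starts on Days 191–196 and takes the last open-label dose by Day 196 is not in the population. If the only open-label dosing day is a Day 196 visit, 4.1.4 excludes the patient, 4.2.5 read by date gives no start, and 4.7 therefore counts nothing. A reaction on Day 196 itself is still a double-blind TEAE, since 196 ≤ 168 + 28.

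**5. Check of the remedy.** Starting the period at the first open-label dose puts all first-day AEs into open-label. With L = 168, however, those on Days 191–196 (6 of 11) would also be in the double-blind window, so a precedence rule is needed. Let O be the day of the first open-label dose and end the double-blind window at min(L + 28, O − 1). For O = 193 this is min(196, 192) = 192, with no overlap. For O = 201 it is min(196, 200) = 196, and 200 − 196 = 4 off-drug days (197–200) stay outside both periods.

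**The case against.** The strongest reply is that 4.2.5 can be read sensibly. Drug handed out at the visit is taken after it, and the period opens on the day of that dose. The Day 1 convention in SAP 4.2.2 has the same order: visit measurements are assumed to precede dosing, and AEs on the first dosing date are treatment-emergent. On that reading no first day is excluded. This stands as a reading, so first-day exclusion cannot be stated as certain. But the SAP works in dates, and version 3.0 lacks the *on or* of version 2.0, so a programmer could apply the strict rule. Even then, a first-day AE that worsens later is counted under 4.7.

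A reader might infer that the affected events vanish. They do not: those up to L + 28 are in the double-blind tables, and section 4.6.2 lists all AEs.

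A reader might also infer that the patients affected are mostly placebo patients new to pirfenidone. The documents support that only for unblinded entrants. Open-label drug is offered to both arms, so completers include patients restarting it.

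Nor is the restriction to completers new in version 3.0, since version 2.0 had it.

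Finally, unblinding is reserved for emergencies, the number of such entrants could be zero, safety data are not formally tested, and no efficacy result is touched. All of this limits the size of the problem. None of it gives unblinded entrants a start date or repairs the population rule.

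**Conclusion.** The concern holds as a fault in definitions that misattributes AEs.

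- **Unblinded entrants:** certain on the text. They have no period start and no open-label AEs, yet may be in the denominator.
- **First open-label day:** possible, and dependent on reading *after* by calendar date.
- **Population rule:** excludes a patient only if open-label drug starts by day 28 and also stops by day 28. The day counts assume that randomised treatment end equals the last randomised dose. For completers they also assume a last dose near Day 168, because their visit is scheduled from randomisation.

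Affected events up to the last randomised dose plus 28 days appear in the double-blind TEAE tables under the randomised arm. The others appear only in the listing, where an AE that fits no period has a missing flag. The documents give no patient counts. The numbers are probably small, and I would not put a rate on them. The fault still deserves correction, because stated rules assign events wrongly and no new data are needed to put it right.

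**What to change.** Make the same change in SAP 4.1.4, 4.2.5 and 4.7:

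1. **Population:** all patients with at least one positive dose in the open-label drug log.
2. **Period start:** the date of that first dose, whether or not double-blind treatment was completed.
3. **Precedence:** in 4.6.2 and the matching windows in 4.2 and 4.2.4, end the double-blind window at the earlier of the last randomised dose plus 28 days and the day before the first open-label dose. No AE onset then falls in two periods. State that onsets in any off-drug gap between the two periods are listed only.

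Version 2.0 already used the first open-label dose as the anchor for post-treatment medications (4.4.4), so the idea is not new to this SAP.

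The cost is a few definitions and a re-run of the safety tables. SAP 4.5.8 dates the primary analysis to March 2019, so any event that the precedence rule moves out of double-blind tables already produced should be footnoted.
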